#### Primary Endpoint

The primary endpoint of the study is that a 25% reduction in  $SUV_{max}$  or  $SUV_{mean}$  for each of the PET imaging tracers will be predictive of increased overall survival. These endpoints will be analyzed by

Kaplan-Meier analysis and logrank tests. Cox proportional hazards regression will also be used to estimate hazard ratios. Each analysis will be performed at the two sided 0.0125 significance level to adjust for four comparisons.

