## 2. BACKGROUND

### 2.1. Malignant Brain Tumors

Despite significant advances in the understanding of brain tumor biology and genetics as well as improvements in surgical techniques, radiotherapy administration, and chemotherapy methods; most primary brain tumors remain incurable. Most primary brain tumors are highly infiltrative neoplasms, and are therefore unlikely to be cured by local treatments such as surgery, focal radiotherapy, radiosurgery, or brachytherapy.

The clinical presentation of a brain tumor is highly dependent on its location within the nervous system; but includes signs/symptoms that relate directly to compression and/or infiltration of specific functional areas of brain parenchyma, increased intracranial pressure, hydrocephalus, cerebral edema, and/or vascular complications from the tumor. The most common symptoms include headaches, cognitive deficits, nausea/vomiting, seizures, balance disturbances, and focal neurologic deficits. Once clinically suspected of having such a lesion, a patient usually undergoes an imaging procedure, typically a computed tomography (CT) scan or a magnetic resonance (MR) scan. Neurosurgical intervention, in the form of either a brain biopsy or craniotomy with resection, is the next step to obtain a tissue diagnosis and, if warranted, to decrease the tumor mass.

There are approximately 16,900 new cases of primary CNS tumors diagnosed in the United States each year. Numerous studies have documented an increase in the incidence of these tumors in the last decades (Sanson-Fisher et al., 2000). About 50% of these lesions are supratentorial high-grade gliomas. Anaplastic astrocytoma (AA) (WHO Grade III) and glioblastoma (GBM) (WHO Grade IV) are the most common glial primary brain tumors with at least 80% of malignant gliomas being GBMs (Brock et al., 1998, Ichimura et al., 1998). Patients with newly diagnosed malignant gliomas are usually treated with biopsy or surgical resection followed by radiation therapy and/or chemotherapy; depending on their functional status. Despite these interventions, the median survivals for newly diagnosed GBM and AA are 50 and 150 weeks, respectively. Chemotherapy has been shown to increase the proportion of long-term survivors from less than 5% to between 15-20 % (Treat et al., 2012). Once a patient has failed initial therapy, salvage therapy is difficult and most patients die of tumor progression within 4-12 months (Group, 2002).

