**Table 3. PET Imaging Biomarkers, Clinical and Biologic Information Database**

PET Imaging Biomarkers a	Clinical and Biologic Information
[  F]FLT (proliferation): SUV max , SUV mean , SUV FLT net , K FLT net	Age at diagnosis, performance status, tumor size and location, radiographic characteristics, extent of surgery, dates and types of therapy.
[  F]Fluciclovine amino acid uptake: SUV max , SUV mean , SUV FLUC , K FLUC net	Tumor histology and WHO grade, vascularity, MIB-1, VEGF, EGFR, p53, IDH status Clinical and radiographic response, concomitant medications; time to progression, overall survival

a Quantitative and semi-quantitative imaging biomarkers

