## 5. TRIAL DESIGN

### 5.1. Patient Eligibility

Two different groups of patients will be able to enroll in the trial. The first group, Group A, will be for patients who have not yet received any therapy for their suspected or newly found brain tumors. Group B will enroll patients with pathologically proven malignant brain tumor (WHO Grade III or IV glial-based tumors) who have undergone chemoradiation and have a contrast enhancing mass ≥ 1.0 cm in greatest diameter concerning for pseudoprogression. MRI-documented possible recurrence/progression versus treatment effect (pseudoprogression) within 6 months from the time of completion of chemoradiation.

Group A will have three different patient cohorts. The first, for patients where there is compelling evidence, based on the MRI and/or CT imaging, that a high-grade primary brain tumor is present. Pathologic confirmation will occur with subsequent biopsy or surgery. The second cohort of patients are individuals where the tumor is felt to be inoperable and a biopsy is performed but no surgery. The third cohort of patients are post-surgery where a complete surgical resection was not possible. This will be confirmed by a post-operative contrast MRI/CT scan where residual tumor  $\geq 1.0$  cm in diameter is present.

Eight to ten patients per year will be enrolled, for a total of 30 patients. Providers within the Radiation Oncology and Neuro-Oncology departments will identify and recruit patients who may be eligible participants.

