With an initial sample size of 30, we estimate that approximately 75% of the subjects (N = 22) will have both a [F]Fluciclovine-PET and [F]FLT-PET after completion of initial chemoradiotherapy. Our justification of sample size is based on data on the prediction of OS using PET reported in Chen et al. (Chen et al., 2007). In this study more than 25% reduction in tumor [F]FLT uptake as measured by standardized uptake value was defined as a metabolic response. In this study there were nine responders (47%) and 10 non-responders (53%). Responders survived three times as long as non-responders (10.8 v 3.4 months;  $P = .003$ ), and tended to have a prolonged progression-free survival ( $P = .061$ ). Both early and later [F]FLT - PET responses were more significant predictors of overall survival (1 to 2 weeks,  $P = .006$ ; 6 weeks,  $P = .002$ ), compared with the MRI responses ( $P = .060$  for both 6-week and best responses). In univariate and multivariate Cox regression analysis, lack of FLT reduction at 6 weeks was the best predictor of reduced OS, with adjusted hazard ratio = 4.955 ( $p = 0.02$ ). Assuming 50% of subjects are metabolic responders, median survival of 3.4 months in non-responders and two years of follow up, a sample size of N = 22 subjects with follow up PET scans will provide 85% power to detect a hazard ratio of 4.9 using a two-sided logrank test at the 0.0125 significance level.

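### The primary survival comparison pools WHO grade III and IV with no stratum or covariate, so it is confounded if grade is linked to SUV response and loses a little power if it is not

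*Combined protocol and SAP*

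**What the plan says.** The primary analysis is set out under Primary Endpoint in section 7.2. Each tracer and SUV measure is to be analyzed by "Kaplan-Meier analysis and logrank tests. Cox proportional hazards regression will also be used to estimate hazard ratios". On the error rate: "Each analysis will be performed at the two sided 0.0125 significance level to adjust for four comparisons". No stratum or covariate is named there or in any other section.

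Section 5.2 admits WHO grade III and IV tumors. Section 2.1 equates anaplastic astrocytoma (AA) with grade III and glioblastoma (GBM) with grade IV, and states that "the median survivals for newly diagnosed GBM and AA are 50 and 150 weeks, respectively". It also puts GBM at 80% or more of malignant gliomas. Table 3 includes "Tumor histology and WHO grade" in the study database.

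Section 7.3 claims that "N = 22 subjects with follow up PET scans will provide 85% power to detect a hazard ratio of 4.9". The planning effect comes from an earlier FLT study in which "lack of FLT reduction at 6 weeks was the best predictor of reduced OS, with adjusted hazard ratio = 4.955". The plan therefore takes its effect size from an adjusted model but specifies no adjusted analysis. Section 7.3 does not say what that model adjusted for.

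**The concern.** Metabolic response is observed after therapy, not assigned. By the protocol's own figures, grade carries a three-fold difference in median survival. If SUV falls by 25% more often in grade III tumors, responders will live longer partly because more of them have grade III disease, and a significant log-rank test could restate what pathology already showed. If response is unrelated to grade, leaving out so strong a prognostic factor weakens the test.

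Whether PET response predicts survival beyond grade is the first thing a reader of a positive result would ask. The plan has no pre-specified answer, which leaves the choice between adjusted and unadjusted results to be made after the data are seen.

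**Working it through.** **1. The plan's own power figure.** Section 7.3 states its inputs as: "Assuming 50% of subjects are metabolic responders, median survival of 3.4 months in non-responders and two years of follow up". With 11 v 11 patients, exponential survival and Schoenfeld's formula, power = Φ(√(D/4) · ln HR − z), where z = 2.498 for two-sided 0.0125 and ln 4.9 = 1.589.
- Exactly 24 months per patient: events = 11 × (1 − 2^(−24/3.4)) + 11 × (1 − 2^(−24/16.66)) = 10.9 + 6.9 = 17.9, and power is 80.5%.
- Two years of follow-up after 36 months of accrual (section 5.1: "Eight to ten patients per year will be enrolled, for a total of 30 patients"): 19.9 events, and power is 85.2%.

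The stated 85% therefore reproduces if follow-up runs after accrual closes. It allows for a single non-responder survival curve and makes no allowance for grade.

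**2. Inputs for the grade check.**
- Weekly hazards: ln 2/50 = 0.0139 (GBM) and ln 2/150 = 0.0046 (AA), a ratio of 3.
- Grade III share: at most about 20%, from section 2.1. That is 22 × 0.20 = 4.4 patients.
- Death within 104 weeks with no response effect: 1 − 2^(−104/50) = 0.763 for grade IV and 1 − 2^(−104/150) = 0.382 for grade III. Expected events are 17.6 × 0.763 + 4.4 × 0.382 = 13.4 + 1.7 = 15.1.
- Response rates by grade: not in the documents. Two assumed pairs are used, 40% v 80% and 35% v 90% (grade IV v III).

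The assumed pairs imply these grade III shares:
- 40% v 80%: responders 0.20 × 0.80 / (0.80 × 0.40 + 0.20 × 0.80) = 0.16/0.48 = 33%; non-responders 0.04/0.52 = 8%.
- 35% v 90%: responders 0.18/0.46 = 39%; non-responders 0.02/0.54 = 4%.

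**3. False positives at nominal 1.25%.** Simulated, N = 22, no effect of response within grade:

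| Scenario | Unadjusted log-rank | Stratified by grade |
|---|---|---|
| Single grade | about 1.8% | same test |
| 20% grade III, response unrelated to grade | 1.8% | 1.8% |
| 20% grade III, response 40% v 80% | 2.7% | 2.0% |
| 20% grade III, response 35% v 90% | 3.8% | 2.2% |

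A second set fixed 11 patients per group and set the grade III share in each directly. It gave 1.7% with a single grade and 1.5% unadjusted with 20% in both groups. With 30% v 10% it gave 2.4% unadjusted and 1.8% to 1.9% stratified. With 40% v 0% it gave 4.7% to 4.9% unadjusted and 2.0% stratified.

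**4. Power at HR 4.9, 20% grade III, response unrelated to grade.** The gain depends on how the medians are anchored:

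| Anchoring of medians | Unadjusted | Stratified |
|---|---|---|
| 50/150 weeks in non-responders | 39% | 40% |
| 50/150 weeks midway between the groups on the log-hazard scale | 57% | 60% |
| Planning scale: 3.4 and 10.2 months in non-responders | 61% | 66% |

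On the planning scale with 11 v 11 fixed, the figures are 63% unadjusted and 68% stratified. A grade-adjusted Cox score test reaches 73%, but its null rejection rate is also higher (1.9% against 1.5% unadjusted), so that gain is not like for like. All grade IV gives 76%. Part of the drop from 76% reflects fewer deaths among longer-lived patients, which stratifying does not recover.

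**5. When grade and response are linked and HR 4.9 is true** (planning scale, 11 v 11). With grade III at 30% of responders and 10% of non-responders, unadjusted rejection is 79% against 64% stratified. With the shares reversed, it is 48% against 66%.

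**The case against.** The strongest objection concerns the question asked. The endpoint is that SUV reduction predicts survival, not that it predicts survival independently of grade. If responders live longer because more of them have grade III tumors, the marginal prediction is still true, and calling it a false positive assumes a different estimand. This stands as a point of definition. It does not remove the need for the grade-adjusted answer, because grade is already known from tissue and the value of a PET marker lies in what it adds.

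Second, the study calls itself exploratory, and sections 4.3, 6.1.2 and 6.2.2 plan to relate SUV change and other biomarkers to histology and clinical data, which could expose an imbalance descriptively. This lowers the severity. It does not supply a pre-specified adjusted estimate for a comparison that carries its own multiplicity-corrected significance level.

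Third, a reader might infer three stronger claims that the documents do not support:
- **That pooling grades in itself inflates false positives.** It does not: with response unrelated to grade the rate is 1.8% either way. No section gives a response rate by grade, or even the direction of a link.
- **That inflation and power loss occur together.** They come from different scenarios. When grade III clusters among responders, unadjusted rejection rises.
- **That false positives reach 4% to 7%.** Under the same response pairs this needs a grade III share of 30% to 35%, and section 2.1 implies about 20% or less.

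Finally, part of the excess over 1.25% is a small-sample property of the log-rank test and would remain after stratifying.

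**Conclusion.** The gap is real and its size is modest. A factor with a three-fold difference in median survival is recorded but left out of a comparison between non-randomized groups.

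At about 20% grade III, a link between grade and response of the assumed strength moves the false-positive rate from about 1.8% to between 2.7% and 3.8%. Stratifying brings it to between 2.0% and 2.2%. Without a link there is no inflation, and stratifying gains about 1 to 5 points of power.

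These figures rest on exponential survival, AA standing for all grade III tumors, 22 evaluable patients, two years of follow-up each, and response rates by grade that are assumptions. With a smaller grade III share the effect shrinks: at 10% and response 40% v 80% the two tests are about equal (1.9% unadjusted, 2.0% stratified).

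The adjusted hazard ratio behind the planning value is a further reason to specify an adjusted analysis. It is not evidence that grade was the factor adjusted for.

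**What to change.** In section 7.2, pre-specify for each of the four primary comparisons a log-rank test and Cox model stratified by, or adjusted for, WHO grade (III v IV), and name which of the two is used. Limit strata to grade. Report the unstratified log-rank test and hazard ratio alongside, and tabulate grade by response group so that any imbalance is visible.

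The cost is a wording change using data already collected. There are two drawbacks. The grade III stratum, about 4 of 22 patients with roughly 2 expected deaths, adds little information. The stratified test also stays slightly above its nominal level at this sample size, which the report should state.

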The data from multiple PET biomarkers combined with histologic and clinical data will enable identification and development of PET biomarker profiles which correlate with (and might be predictive of) tumor aggressiveness and clinical outcomes. The three imaging time point assessments serve multiple uses in this initial exploratory study. If baseline imaging can predict tumor aggressiveness and clinical outcomes, such imaging may potentially be used to guide selection of conventional, aggressive, or investigational therapies. The second time point, within 1-4 weeks after 6wks of chemoradiotherapy, will provide a measurement of tumor response that may potentially differentiate tumors that will progress rapidly from those that will not (changes in imaging biomarkers between exams 1 and 2 will likely be important for this determination). Finally, the multi-tracer array at the time of treatment effect (pseudoprogression) versus true recurrence/progression may yield new insights into the physiology and biology of these tumors, and multi-tracer imaging may help to differentiate recurrence from radiation necrosis/treatment effect (pseudoprogression). We believe the complementary value of the two tracers in conjunction has much greater potential for meeting these goals than any one tracer alone. For example, tumors with high proliferation ([F]FLT) and/or growth ([F]Fluciclovine) may respond best to anti-EGFR-directed agents or conventional cytotoxic chemotherapies. Of specific interest, is there a multi-tracer PET signature that distinguishes between treatment effect (pseudoprogression) and true progression/recurrence that will have important clinical utility? These questions will be studied in detail, developing formal hypotheses that will be tested in future phase II/III clinical trials.

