#### 6.1.2. [F]FLT Semi-Quantitative Assessment

Semi-quantitative assessment of [F]FLT uptake will be performed by calculating  $SUV_{max}$  and  $SUV_{mean}$ . A region-of-interest (ROI) will be drawn over any tumor mass, necrotic region, or other abnormal region(s) on the summed static [F]FLT PET image. For each ROI, standardized uptake values (SUVs) with body surface-area correction will be obtained for both the maximum and mean voxel value in ROI:

$$SUV_{max} = \frac{A_{max}}{InjectedDose/BSA} \quad SUV_{mean} = \frac{A_{mean}}{InjectedDose/BSA}$$

$$BSA = W^{0.425} \times H^{0.725} \times 0.00718$$

$A_{max}$  = maximum voxel value in ROI ( $\mu$ Ci/mL; mCi/L; or MBq/L)

[figure not shown]
$A_{mean}$  = mean voxel value in ROI ( $\mu$ Ci/mL; mCi/L; or MBq/L)

$BSA$  = body surface area, computed from height H (cm) and weight W (kg)

Ratios of the SUV of tumor to that of white matter (T/WM) and cortex (T/C) will also be computed. The change in SUVs for pre-treatment (baseline) and post-treatment images will be computed and correlated with available histologic and clinical data.

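### The primary survival comparison by 25% SUV reduction carries no baseline-SUV term, so its hazard ratio cannot separate a fall in uptake from a high or low starting level

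*Combined protocol and SAP*

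**What the plan says.** Section 7.2 (Primary Endpoint) sets out to show that a 25% fall in SUVmax or SUVmean "for each of the PET imaging tracers will be predictive of increased overall survival". The methods are "Kaplan-Meier analysis and logrank tests", followed by "Cox proportional hazards regression will also be used to estimate hazard ratios". On error control: "Each analysis will be performed at the two sided 0.0125 significance level to adjust for four comparisons". No stratification factor or covariate is named there, and no other section adds one to the primary model.

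Section 6.1.2 derives the response variable for FLT: "The change in SUVs for pre-treatment (baseline) and post-treatment images will be computed and correlated with available histologic and clinical data". Section 6.2.2 does the same for fluciclovine. Every patient who can be classed as a responder or non-responder therefore has a baseline SUV for that tracer and metric.

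The text after Table 3 in Section 4.3.1 raises baseline uptake as a prognostic marker in conditional terms: "If baseline imaging can predict tumor aggressiveness and clinical outcomes", it could help to guide the choice of therapy.

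Section 7.3 sizes the trial on an unadjusted two-sided log-rank test: N = 22, half of them responders, a 3.4-month median in non-responders, two years of follow-up, a hazard ratio of 4.9 and 85% power. The 4.9 comes from an adjusted Cox estimate of 4.955 in the cited FLT study. The adjusting variables are not listed.

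**The concern.** A percentage fall depends on where uptake started. Regression to the mean and a floor at background uptake would make a 25% fall easier from a high baseline. Tumour biology could work the other way, with low-uptake tumours responding more often. If baseline uptake also carries prognosis, responders and non-responders differ in two respects: how far uptake fell and where it began. A single-term Cox model gives one number for both.

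At stake is the interpretation of the result. A reader of a positive primary result will want to know whether the post-treatment scan adds anything to the baseline scan, and the planned analysis cannot say. This applies to all four primary comparisons. It carries over to the secondary objectives in Section 7.2, where PET is set against MRI by informal comparison of hazard ratios and p-values.

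**Working it through.** **The plan's own figure.** Take 11 patients per group, exponential survival with medians 3.4 and 3.4 × 4.9 = 16.7 months, and 36 months of accrual (30 patients at 10 per year, Section 5.1) followed by 24 months.
- Hazards: ln 2/3.4 = 0.204 and 0.204/4.9 = 0.0416 per month.
- Expected deaths per group: 11 × {1 − [exp(−24λ) − exp(−60λ)]/(36λ)}, giving 10.99 + 8.90 = 19.9.
- Schoenfeld power: Φ(√(19.9/4) × ln 4.9 − 2.498) = Φ(3.544 − 2.498) = 85.2%.

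The stated 85% reproduces. With exactly 24 months per patient there are 17.9 deaths and the formula gives 80.5%. Simulated log-rank power is 76.6% (24 months each) or 77.9% (with accrual). About 77% is therefore the reference for the simulated powers below.

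**Assumed inputs.** The documents give neither the baseline hazard ratio per SD nor the correlation r between baseline SUV and the tendency to respond. Positive r means that high-uptake tumours respond more. I take baseline hazard ratios of 1.25, 1.5 and 2.0 and r from −0.5 to 0.5.

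**Model.** The hazard is λ × 4.9^(non-response) × HR_b^b, where b is standardised log baseline SUV and follow-up stops at 24 months. In the N = 22 runs the half with the largest falls are the responders. The adjusted test is the Cox likelihood-ratio test with b in the model. Hazard ratios are non-responder over responder.

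| r | Large-sample unadjusted HR, baseline HR 1.25 / 1.5 / 2.0 | Median unadjusted HR, N = 22, baseline HR 1.5 | Log-rank power | Adjusted power |
|---|---|---|---|---|
| 0.5 | 3.9 / 3.2 / 2.3 | 3.4 | 47% | 64% |
| 0.3 | 4.2 / 3.6 / 2.7 | 3.7 | 56% | 70% |
| 0 | 4.6 / 4.3 / 3.5 | 4.45 | 67% | 72% |
| −0.3 | 5.2 / 5.1 / 4.7 | 5.3 | 78% | 68% |
| −0.5 | 5.4 / 5.9 / 6.0 | 6.2 | 85% | 65% |

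Powers are at two-sided 0.0125 with baseline HR 1.5. In large samples the adjusted model returns 4.7 to 5.1 throughout. At N = 22 its median is about 5.5, which is small-sample upward bias; the unadjusted median with a non-prognostic baseline is 5.1 to 5.3. At r = −0.3 the two influences nearly cancel.

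**If baseline is not prognostic.** Log-rank against adjusted power is 77% v 74% at r = 0, 76% v 71% at r = 0.3 and 76% v 64% at r = 0.5. Monte Carlo error is about one point (√(0.75 × 0.25/2000) = 1.0%). Repeated runs put the loss at about 4 to 6 points for weak correlation and about 12 for strong.

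**No response effect given baseline, baseline HR 2.0.** The nominal rate in each direction is 0.0125/2 = 0.625%.
- r = 0.3 to 0.5: the log-rank test rejects in about 4.0% to 6.9% of trials, but only 0.0 to 0.3 points of that favour responders. The rest show responders dying sooner.
- r = −0.5: rejections in favour of responders reach about 6.6%.

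The large-sample unadjusted hazard ratio under this null runs from 0.64 (r = 0.5) to 1.53 (r = −0.5).

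**The case against.** **The primary question is marginal.** Sections 4.3.1 and 7.2 ask whether the 25% rule predicts survival. The unadjusted log-rank test answers that validly, and it is the test powered in Section 7.3. When r is not zero, a survival difference carried by baseline uptake is a real marginal difference. The 6.6% above is a false positive only for the claim that the fall itself is informative. At r = 0 the smaller unadjusted hazard ratio reflects non-collapsibility, not bias. All of this stands, and it is why the log-rank test should remain primary.

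**The inputs are assumed.** A reader might infer that the protocol expects high baseline uptake to mean shorter survival. It does not say so: the sentence in Section 4.3.1 begins with a conditional and gives no direction. A reader might also infer that omitting baseline always dilutes the effect, or that it inflates false claims of benefit. The table and the null runs show that both depend on the sign of r.

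**The power gap treats 4.9 as conditional on baseline SUV.** The source estimate is adjusted, but its covariates are not listed, so baseline SUV cannot be presumed among them. If 4.9 is already the marginal value, the power losses at positive r disappear. The 85% is not shown to be wrong on this account.

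**The adjusted test is slightly oversized** (1.4% to 2.9% under the null). This does not explain its advantage at positive r: calibrated to 1.25%, it still had 64% power against 57% for the uncalibrated log-rank test at r = 0.3 and baseline HR 1.5.

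**Why baseline SUV and not age, grade or IDH?** With this many deaths only one extra term is comfortable, and baseline SUV is the one from which response is calculated.

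**The trial is exploratory.** True, and that limits the weight of the point. It does not remove the value of fixing the model in advance.

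**Conclusion.** The point holds as a gap in interpretation. The plan names no baseline term, although the response variable is built from baseline SUV and baseline uptake is itself put forward as a possible predictor. If baseline is prognostic and correlated with response, the planned hazard ratio does not isolate the fall.

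The size rests wholly on assumed inputs. With a baseline hazard ratio of 1.5 per SD, a true conditional 4.9 is estimated at a median of 3.4 to 6.2 as r runs from 0.5 to −0.5. If baseline is not prognostic, nothing is distorted. A raised rate of wrongly crediting the fall with longer survival (about 6.6%, baseline hazard ratio 2.0) arises when low-uptake tumours respond more. In the opposite case the errors point to shorter survival in responders.

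The documents do not support calling the log-rank test invalid, calling the stated power wrong for this reason, or moving the primary claim to an adjusted model.

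**What to change.** In Section 7.2, keep the Kaplan-Meier curves and the log-rank test at 0.0125 as the primary test of the marginal question. Then add wording such as this:

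*For each of the four primary comparisons, a supportive Cox model will include log baseline SUV (same tracer, same metric) as one continuous covariate. Its hazard ratio and confidence interval will be reported beside the unadjusted ones. A statement that the fall in uptake predicts survival beyond baseline uptake will be made only if the adjusted estimate supports it.*

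This needs no new data. The cost is one more parameter with about 18 to 20 deaths, and a wider interval. The adjusted test has about 4 to 6 points less power if baseline is not prognostic and only weakly correlated with response, and about 12 points less if strongly correlated. At r = −0.5 with a prognostic baseline it has about 20 points less than the unadjusted test, whose effect is overstated there. Because the log-rank test stays primary, these losses affect only the supportive claim.
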